Exclusion Criteria	 Previous treatment with long-term macrolides in the past 3 months. Unable to be investigated with HROM due to contraindications such as anatomical abnormalities or diseases of the oesophagus or unwilling/unable to be investigated with HROM based on the clinical judgement of the investigators due to severity of lung disease. Have another cardiorespiratory cause for their symptoms (such as heart failure or lung cancer). Are unable or unwilling to consent to or complete the trial procedures. Women of child bearing potential not using effective means of contraception. Effective methods of contraception include any oral contraceptive pill, any intrauterine device, any long term contraceptive implant, and any long-acting contraceptive injection Have been involved in another medicinal trial (CTIMP) within past four weeks.

Trial Treatment(s)	Trial Participants will be commenced on azithromycin therapy as part of usual clinical care.
Trial Endpoints and Statistical Methods	For trial endpoints, appropriate statistical analysis will be performed to compare HROM metrics and symptom questionnaire data at baseline and at follow-up.
	A table showing baseline demographic and clinical characteristics for each group will be presented. Participant characteristics will be summarised using appropriate statistics. Medians (interquartile range) will be reported for ordinal data, mean (standard deviation) for continuous data and raw count (number, %) will be reported for nominal data.
	For participant outcome data, descriptive statistics, mean (standard deviation) for continuous outcomes and raw count (%) for categorical outcomes, will be reported for each group at baseline and at 1-month follow-up, and for continuous objective and subjective cough data where applicable.
Safety Analyses	AEs/SAEs will be listed and summarized using descriptive statistics.
Sample Size Rationale	As this is a pilot study, a formal sample size calculation has not been performed. We will recruit 30 participants over 12 months based on National Institute for Health Research recommendations for pilot/feasibility studies.

SCHEDULE OF ASSESSMENTS AND PROCEDURES

Visit	Screening Visit	Baseline visit		Follow up visit
Day	-28 to -7	0		28 to 42
Procedure/Assessment			mi i	
Written Informed Consent	Х			
Inclusion/ Exclusion Criteria	Χ	Х		
Invitation Experience survey	Χ			
Setup of the Hyfe Cough Tracker©	Χ			
Monitoring of cough frequency using the Hyfe Cough Tracker©	X**	Х		Х

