2. TRIAL AIMS AND OBJECTIVES

Aim: To investigate the feasibility and acceptability of HROM in the diagnosis and treatment strategies of chronic respiratory diseases. Exploratory analysis will be performed on the effect of azithromycin on oesophageal motility and how it relates to symptomatic improvement in patients with chronic respiratory disease who are being commenced on azithromycin as part of routine clinical care.

Objectives: Specific trial objectives will address both the feasibility and acceptability outcomes as well as exploratory outcomes.

Feasibility outcomes

- 1. Recruitment: eligibility to consent ratio, recruitment rate, and participant retention to follow-up.
- 2. Data quality: Completion of clinical outcomes at follow-up and patterns of missing data for the trial measures. Completion of participant symptom questionnaires throughout the study. Completion of trial processes, principally HROM.
- 3. Acceptability of assessment: Quantify the proportion of participants who judge the trial investigations, principally HROM, to be acceptable.

Exploratory clinical outcomes

- Oesophageal function: To evaluate the effect of azithromycin on oesophageal contraction vigour and swallow coordination. This will be evaluated by investigating participants with HROM before and 1 month after initiation of azithromycin as part of routine clinical care.
- Symptom burden: Symptoms will be assessed before and 1 month after initiation of azithromycin as part of routine clinical care. Symptoms will be measured using validated symptom questionnaires, visual analogue scale for cough, and numeric rating scales for breathlessness
- 3. Relationship between oesophageal motility and symptoms: The change in oesophageal functioning and presence of respiratory symptoms will be examined in each participant. The relationship between these two parameters will then be examined using statistical analysis.

4. Effect of azithromycin therapy on continuous objective cough frequency as measured by the Hyfe Cough Tracker©.

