3. TRIAL DESIGN

A prospective observational trial evaluating the effect of 1 month (up to 6 weeks) of azithromycin treatment on oesophageal motility and symptom burden in patients with chronic respiratory disease who are being commenced on azithromycin as part of routine clinical care. Participants will be investigated using HROM before and during treatment with azithromycin to evaluate the change in oesophageal function.

The trial team will not be prescribing the azithromycin treatment for the participants, as this will be the decision and the responsibility of their usual treating clinician. However, it is anticipated that all participants will be treated with azithromycin 250 milligrams once daily or three times per week throughout the duration of the study. The acceptability of HROM as a diagnostic tool will be assessed through participant experience surveys. We will also analyse other feasibility outcomes such as eligibility to recruitment ratio and participant retention rate to ascertain how willing participants will be to engage in all trial procedures to inform larger clinical trials/ mechanistic studies.

Participants will be investigated with validated questionnaires to ascertain their symptom burden before and during treatment with azithromycin. With this information we will correlate changes in oesophageal function and symptom burden in this group of patients. Participants will also be asked to use the Hyfe Cough Tracker© equipment (to be further determined - if a dedicated smartphone running the application or a wearable smartwatch running the application) for at least one week prior to their initiation of azithromycin and for the duration of their azithromycin treatment whilst in the trial. We will then observe the difference between daily cough counts before and after azithromycin treatment and be able to ascertain how this correlates with oesophageal function. Additionally, we will look into the relationship of objective cough frequency data and repetitive subjective cough evaluation using cough VAS.

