11. STATISTICAL METHODS

The primary feasibility outcomes will consist of recruitment rate, retention rate, adverse events, compliance, and acceptability of the HROM assessment. The recruitment rate, consisting of the eligibility and consent rate will be calculated with 95 % confidence intervals (CI). A table showing baseline demographic and clinical characteristics for each group will be presented to indicate any differences between groups. Participant characteristics will be summarised using appropriate statistics. Medians (IQR) will be reported for ordinal data, mean (standard deviation) for continuous data and raw count (number (%) will be reported for nominal data.

For the clinical outcomes, all HROM data will be recorded, and median metrics will be recorded for the overall participant cohort and will be broken down into smaller categories based on primary respiratory diagnoses. Questionnaire data will be reported for all participants and mean scores will be reported. A table showing baseline demographic and clinical characters will be presented. Participant characteristics will be summarised using appropriate statistics. Medians (IQR) will be reported for ordinal data, mean (standard deviation) for continuous data and raw count (number [%]) will be reported for nominal data.

Comparison of baseline and follow-up HROM and questionnaire data will be made using paired ttests for normally distributed data and Mann-Whitney U testing for skewed data. Averages of all

HROM metrics and questionnaire data will be presented in tables and p-values of the statistical tests will be displayed alongside this data.

Safety data will be summarised using descriptive statistics.

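### Section 11 reports exploratory results as visit averages with p-values, not as within-participant change with its precision, and Objective 3 does not match the correlation of changes described in Section 3

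*Protocol*

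**What the plan says.** **Reporting.** Section 11 of the Protocol summarises HROM metrics by medians (overall and by primary diagnosis) and questionnaires by mean scores. On testing it says "Comparison of baseline and follow-up HROM and questionnaire data will be made using paired" t-tests when data are normal, and "Mann-Whitney U testing for skewed data". The output is then fixed: averages of every HROM metric and questionnaire score are tabulated, and "p-values of the statistical tests will be displayed alongside this data". The only confidence interval named in Section 11 is for the recruitment rate. The Protocol Synopsis likewise summarises outcomes separately at baseline and at one month, with mean (SD) for continuous outcomes.

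**Size.** The Synopsis states that "a formal sample size calculation has not been performed" and that "We will recruit 30 participants over 12 months".

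**Who has both HROM tests.** Under Section 4.4, participants who stop azithromycin do not repeat HROM, and those who decline a second HROM stay in for everything else.

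**Motility and symptoms.** Exploratory objective 3, in the Synopsis and in Section 2, reads: "The change in oesophageal functioning and presence of respiratory symptoms will be examined in each participant". Section 3 reads: "With this information we will correlate changes in oesophageal function and symptom burden in this group of patients". Sections 6.3.1 and 6.3.2 say that HARQ and BCSS differences will be correlated with HROM findings. Section 11 names no analysis of the relationship.

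**The concern.** The exploratory question is how far each person changes on azithromycin. The informative result is the within-participant change and its precision. The stated output is two visit averages and a p-value per measure. With no power basis, a small p-value is easily read as efficacy and a large one as no effect, while neither reader sees how wide the uncertainty is. Anyone designing a later study on these measures needs the SD of change, and it is not among the planned outputs.

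Objective 3 raises a separate problem. Its wording pairs a change with a state (presence of symptoms), while Section 3 pairs a change with a change. These are different analyses, and Section 11 does not say which one is done.

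**Working it through.** The Protocol gives no power, effect size, SD or alpha, so it has no figure to reproduce. The check asks what can be recovered from the stated output. Inputs: n = 30 from the Synopsis; 24 and 20 complete pairs and the between-visit correlation ρ are assumptions.

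**1. Normal data, complete pairs.** The difference of the two visit means equals the mean paired change. The interval can be recovered from an exact paired-t p-value. Example: difference 5, p = 0.04, n = 30. The t value for p = 0.04 on 29 df is 2.150, so SE = 5/2.150 = 2.33, and the 95% CI is 5 ± 2.045 × 2.33, or 0.24 to 9.76. In this branch the defect is in reporting only.

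**2. Medians.** A difference of medians is not the median change. If two of three people each move up one rank and the third falls from top to bottom, the two visit medians coincide although the median change is a rise.

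**3. Unequal sets.** Participants with only a baseline HROM enter the first average and not the second, so the two averages can describe different people. Section 5.2 excludes from analysis those who curtail azithromycin, which may remove the discontinuers. It does not remove those who only decline the second HROM.

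**4. SD of change.** With equal visit SDs, SD_change = SD × √(2(1 − ρ)), and the 95% half-width is t(0.975, n − 1) × SD_change/√n.

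- In units of SD_change: 0.37 at n = 30, 0.42 at n = 24, 0.47 at n = 20.
- In units of the visit SD at n = 30:

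| ρ | √(2(1 − ρ)) | half-width |
|---|---|---|
| 0.3 | 1.18 | 0.44 |
| 0.5 | 1.00 | 0.37 |
| 0.7 | 0.77 | 0.29 |
| 0.9 | 0.45 | 0.17 |

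Visit means and SDs do not reveal ρ. The variance of change is proportional to 2(1 − ρ), which runs from 1.4 to 0.2 over this range. A later study sized on change would therefore differ by a factor of 1.4/0.2 = 7.

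**5. Skewed data.** Mann-Whitney U treats the two visits as independent groups. Simulation used lognormal data, n = 30, ρ on the log scale, a two-sided 0.05 level and a shift of 0.4 log-SD for power. There were 5,000 runs for Mann-Whitney and 2,000 for the signed-rank test on log differences.

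| ρ | Mann-Whitney type I error | Mann-Whitney power | signed-rank power |
|---|---|---|---|
| 0.3 | 0.019 | 0.29 | 0.43 |
| 0.5 | 0.007 | 0.25 | 0.54 |
| 0.7 | 0.001 | 0.22 | 0.75 |

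Ignoring the pairing makes the test conservative and costs power.

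**6. Change against change.** Fisher interval: tanh(atanh r ± 1.96/√(n − 3)). At n = 30 an observed r = 0.3 gives −0.07 to 0.60, and r = 0.5 gives 0.17 to 0.73. The rewording will not narrow these intervals; they show why a correlation should not be reported without one.

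**The case against.** Much can be said for the plan.

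- **The paired change is addressed.** A reader might infer that it is not estimated at all. That is too strong: the paired t-test targets it, and step 1 shows that its interval is recoverable for complete normal data. The individual paired data are also collected, so the SD of change can be computed later. This limits the point to what is reported, plus the test for skewed data.
- **The change-change association is planned.** A reader might infer from Objective 3 that it is not. Section 3 states it, Sections 6.3.1 and 6.3.2 point the same way, and the aim speaks of symptomatic improvement. Objective 3 can even be read as change in both. What stands is an inconsistency of wording that Section 11 does not settle.
- **Objective 3 is not unanswerable.** One might argue that presence cannot vary because everyone enters with HARQ of at least 14. That is an entry criterion only. HARQ is repeated at follow-up and may fall below 14.
- **Multiplicity.** Counting 3 HROM metrics, 6 general scores and 5 diagnosis-specific scores gives 14 tests, and 1 − 0.95^14 = 0.51. This is at most an upper illustration under independence. The symptom scores overlap, the diagnosis-specific scores are given according to primary diagnosis, and Mann-Whitney U on paired data is conservative.
- **Purpose and SAP.** Section 3 ties informing larger trials to the feasibility outcomes, not to an SD of change. Correlation coefficients and interval methods are commonly left to an SAP. The point therefore rests on the output and test that Section 11 does state, and on two Protocol sections that disagree.

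**Conclusion.** The point holds in a limited form. Section 11 commits to visit averages with p-values for exploratory outcomes in a pilot of 30 with no power basis. For HROM medians, skewed data and incomplete HROM pairs, those averages do not give the within-participant change; visit summaries alone do not give its SD in any branch. Depending on an unreported between-visit correlation (assumed 0.3 to 0.9), the half-width at 30 complete pairs lies anywhere from 0.44 to 0.17 visit SDs. Objective 3 and Section 3 describe different analyses, and Section 11 carries neither.

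The documents do not support saying that change or the association is left unestimated, nor that the diagnosis-specific scores are bound to be uninformative: no split by diagnosis is given.

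Severity is minor to moderate, because Section 6.1 makes feasibility and acceptability primary. The simulated figures depend on the lognormal model and the chosen shift.

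**What to change.** 1. **Section 11 and Synopsis.** For each HROM metric and questionnaire score, report the number with both visits and, on those participants, the paired mean or median change with its 95% CI and the SD of change. Visit averages can stay beside them.
2. **Skewed data.** Replace Mann-Whitney U by a paired method, for example the Wilcoxon signed-rank test with a Hodges-Lehmann estimate and interval.
3. **P-values.** If kept, label them exploratory.
4. **Objective 3 (Synopsis and Section 2).** Reword it to match Section 3: change in HROM metric against change in symptom score, reported as a correlation with 95% CI. Name that analysis in Section 11.

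The cost is wording in three places and a little extra analysis on data already collected. The downside is less emphasis on p-values. Which HROM metric and which score should lead is for the investigators to choose.

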12. TRIAL MANAGEMENT

12.1 Trial Oversight

Hull University Teaching Hospitals NHS Trust will act as sponsor for the study. There will be a trial management group (TMG) set up to oversee the operation of the study.

Membership details of these committee:

The TMG consists of the Principal Investigator ([name]) and other trial investigators [name], [name], and [name]. The TMG will meet before recruitment begins, and every 3 months. Additional meetings will be arranged if required. The TMG will oversee progress and achievement of milestones. Minutes of the meetings will be stored in the Investigator Site File.

These committees will function in accordance within standard operating procedures/NIHR terms of reference.

132. PROCEDURES AND INSTRUCTIONS (ADMINISTRATIVE PROCEDURES)

13.1 Ethics

The protocol, participant information leaflet (PIL), informed consent form (ICF) and appropriate related documents must be reviewed and approved by a REC. Any protocol amendment and/or revision to the PIL or ICF will be resubmitted to the REC for review and approval (except for changes involving only logistical or administrative aspects of the study).

A signed letter of trial approval from the REC Chairman must be sent to the Principal Investigator with a copy to the Sponsor prior to trial start. If the REC decides to suspend or terminate the study, the Investigator will immediately send the notice of trial suspension or termination by the REC to the Sponsor.

Trial progress is to be reported to RECs as required by the Investigator(s) or Sponsor, depending on local regulatory obligations. If the Investigator is required to report to the REC, they will forward a copy to the Sponsor at the time of each periodic report. The Investigator or the Sponsor will submit, depending on local regulations, periodic reports and inform the REC of any reportable AEs as per ICH guidelines and local REC standards of practice. Upon completion of the study, the Investigator will provide the REC with a brief report of the outcome of the study, if required.

13.2 Participant Information and Informed Consent

As part of the informed consent process, the Investigator must explain to each participant the nature of the study, its purpose, the procedures involved, the expected duration, the potential risks and benefits involved, and any potential discomfort. Each participant must be informed that participation in the trial is voluntary and that he/she may withdraw from the trial at any time and that withdrawal of consent will not affect his/her subsequent medical treatment or relationship with the treating clinician.

This informed consent should be confirmed by the signing of the REC approved consent form by the participant. The participant should understand the information in the participant information leaflet and the statements on the consent form before signing and dating it. The participant will be given a copy of the signed form. The participant will be asked to sign the consent form prior to any study-specific procedures being performed.

The form must be signed and dated by an appropriately trained member of the research team directly after the participant has signed. A copy of the signed ICF will be given to the participant and a copy will be filed in the participant's medical records. The original signed ICF for each participant will be kept in the Investigator Site File.

The participant should be informed in a timely manner if new information becomes available that may be relevant to the participant's willingness to continue participation in the trial. The communication of this information should be documented.

13.3 Discontinuation/Withdrawal of Participants from Study

Each participant has the right to withdraw from the study at any time. In addition, the investigator may discontinue a participant from the study at any time if the investigator considers it necessary for any reason including:

Pregnancy

- Ineligibility (either arising during the study or retrospective having been overlooked at screening)
- Significant protocol deviation
- Significant non-compliance with treatment regimen or study requirements
- An adverse event, which requires discontinuation of the study medication or results in an inability to continue to comply with study procedures
- Consent is withdrawn
- Lost to follow up
- Loss of participant mental capacity to follow the trial protocol

If the participant withdraws consent, no further trial activity will occur, and any samples will be destroyed and the reason for withdrawal will be recorded in the CRF.

As part of the consent process the participant will be asked if all data collected up until the time of withdrawal can be used as part of the study results. If the participant is withdrawn due to an adverse event, the investigator will arrange for follow-up visits or telephone calls until the adverse event has resolved or stabilised. Their data may still be used for analysis.

13.4 Changes to the Protocol

There are to be no changes to the protocol without written approval from the Sponsor. Protocols will be followed as written.

Any substantial change to the protocol requires a written protocol amendment that must be approved by the Sponsor before implementation. Amendments specifically affecting the safety of participants, or the scientific quality of the trial require additional approval by the REC and HRA. These requirements should in no way prevent any immediate action from being taken by the Investigator(s), or by the Sponsor, in the interest of preserving the safety of all participants included in the study. If an immediate change to the protocol is felt by the Investigator(s) to be necessary for safety reasons, the Sponsor must be notified promptly and the REC must be informed as soon as possible.

Changes affecting only administrative aspects of the trial are known as non-substantial amendments and only require notifying to the HRA.

The Investigators will conduct the trial in strict accordance with the protocol.

13.5 Monitoring Procedures

The Sponsor representatives (HUTH R&D QA staff) will maintain contact with the Investigator(s) and designated staff by email or telephone between trial visits. Monitoring visits to the investigational sites will be conducted by the HUTH R&D monitor. The Investigators will allow the monitor to view the clinical facilities to assure compliance with the regulations and GCP. The CRFs and participant's corresponding original medical records (source documents) are to be fully available for review by the R&D monitor at regular intervals. These reviews are to verify adherence to the protocol and data accuracy in accordance with the regulations and GCP.

The trial will be monitored in accordance with HUTH R&D department's standard operating procedures to ensure compliance with UK Clinical Trial Regulations and ICH GCP. All trial related documents will be made available upon request for monitoring by R&D monitors and for inspection by the MHRA.

Protocol non-compliance are departures from the approved protocol.

Prospective, planned deviations or waivers to the protocol are not allowed under the UK regulations for Clinical Trials and therefore will not be permitted for this trial.

Accidental protocol deviations can happen at any time. If they occur they must be documented on the Protocol Deviation Log and reported to the Sponsor

